6.2.3 Blinding

For this study, participants will not be blind to the condition they are receiving given the fact that the PPMI condition and the EUC condition are of varying lengths (8 sessions vs. 2 sessions). Despite this, we are confident that the nature of the EUC condition (e.g. a study therapist providing education and support to those with chronic pain engaged in OUD treatment) will produce enough of a supportive effect to provide a strong test of the added benefits of PPMI above and beyond the care typically delivered in the community. Study therapists who deliver the condition will not be blind due to the fact that they will be delivering both conditions. Therapists will, however, be trained and instructed to provide a similar level of attention to each participant during the session, regardless of treatment condition.

Data collectors responsible for the collection of follow-up data (post-enrollment data) (i.e. research assistants, project managers, or other study staff) will remain blind to the treatment condition assignment to ensure accurate and unbiased collection of trial outcomes. It is important to note that the primary outcome of interest (retention on buprenorphine treatment over 3-months post enrollment) will be collected via participant self-report through weekly surveys. Therefore, study staff will not be directly involved in the collection of those outcome data. Longitudinal data of the primary outcome (retention on buprenorphine treatment over 12-months post enrollment) will be collected by research study staff via researcher administered interview, and therefore these study staff will remain blind to the assigned treatment condition. In the event that longitudinal data may need to be reviewed for accuracy and coding following collection through case consultation meetings, outcome adjudicators, including investigators or project consultants will be blind to condition assignment to ensure unbiased coding of data. Importantly, the data managers and data analysts will remain blind to study condition when conducting all analyses.

6.2.4 Follow-up Visits

Participants will be asked to complete several different activities following randomization and condition delivery and are described in detail below.

Post-treatment survey. This survey will ask general questions about their experiences with both the study therapist (therapeutic alliance) and the session content. We have used similar measures tapping such constructs in prior research. This survey will be used as a supervision training tool for the therapists and research staff and as data for future intervention refinement purposes. In order to ensure participant privacy and encourage honest responses, research study therapists will not have access to the data collected via

the post-treatment surveys. The survey will be given once at the participant's first follow-up after completion of treatment sessions.

Session Attendance. Attendance of the condition sessions will be monitored to determine whether participants will utilize these therapies. Attendance will be tracked utilizing the Session Contact Form by each research study therapist or research staff at each session and attendance records will be consolidated to determine number of consecutive weeks in which sessions were attended and the total number of sessions attended by each participant.

Weekly Surveys. Following completion of the baseline (enrollment) assessment, participants will be asked to complete a survey once a week for the next 13 weeks (i.e. a total of 3-months post enrollment). These surveys will ask questions regarding pain level, pain functioning, buprenorphine treatment engagement, substance use, and some general questions about health and well-being and should take approximately 5-10 minutes to complete. Participants may be sent an e-mail from REDCap once per week asking them to complete the brief survey. The e-mail will contain a link to the REDCap platform where the participants may complete the survey. Participants will have 6 days from the time the e-mail is sent to complete the survey via REDCap. Participants may receive a system generated or study specific reminder e-mail to complete the survey before the link expires. Participants will not be allowed to complete a previous week's survey once a new link has been sent. This process will be repeated each week for the first 13 weeks of the study. Participants also have the option to complete the surveys over the phone. Research assistants will read the survey questions and record the participants answers in the REDCap survey. Following the completion of each weekly survey, participants will receive \$10 or \$130 for all 13 weeks. If a participant completes all 13 weekly surveys, they can earn an additional \$10 payment, for a possible total possible compensation of \$140 if all weekly surveys are completed.

Study Follow-up Time points. Full study follow-up assessments will be conducted at 1-, 3-, 6-, 9-, and 12-months post study enrollment and will utilize a combination of measures from the eligibility screening survey and baseline assessments (see Section 6.1 "Schedule of Events" for specific measures). These follow-up visits will be completed in-person, whenever possible, by phone, by video chat, or by email. Assessments are expected to take approximately 90 minutes each. Participants will have the option to complete a voluntary urine test at all follow up time points. The urine drug screening may be conducted in-person or at home by mailing the test kit to the participant. At each of the 1-, 3-, 6-, and 9-month follow-up assessments, participants will receive \$40 for completing the assessment, with an additional \$10 possible if they provide a urine sample for testing. Participants will receive \$50 at the 12-month follow-up for completing the assessment, with an additional \$10 for a urine sample. Participants who complete all study follow-up assessments could be compensated up to \$260 total.

Follow-up assessments will take place in-person at the treatment clinic or another location of convenience in the community (e.g., participant's homes, ED, library, fast food restaurants) whenever possible, however assessments may also take place (1) online via REDCap survey, (2) over the phone, (3) over video chat, or (4) through a mailed paper survey where participants can complete surveys on their own and send back to research staff with a follow-up phone interview to complete the assessment. If follow-up assessments are

completed in-person outside of a study location, we will typically arrange for at least two research staff members to go together for safety reasons. All research staff will be required to follow study check-in procedures when conducting follow-up assessments. When meeting participants in public locations for assessments efforts will be made to ensure that others cannot overhear conversation between the participant and study staff, including maintaining sufficient physical distance with others and choosing locations that are not too crowded or busy. Percent of urines positive for substances and buprenorphine at each follow-up will be used to validate self-report measures of abstinence from substances and buprenorphine retention, however these tests will not be utilized as primary outcome data. We have extensive experience using similar methods in our prior work and previous research has shown that the validity of self-report of illegal drug use may be increased when a urine drug screen is also performed.

In order to ensure an adequate completion rate for the post-treatment follow-ups, we will use a series of strategies to locate participants that have been used successfully in our previous research. Using similar strategies, we typically achieve 12-month follow-up retention rates of over 80%. These strategies include utilizing a multi-faceted contact approach which includes contacting participant by mail, phone, in-person, and electronically where permitted, providing participants with reminder phone calls before appointments, and encouraging continuity of contact with individuals on the research team. As part of retention strategies, research staff will be trained in the importance of rapport-building with participants and professional boundaries. The research staff will contact the participants using the contact information provided at the baseline assessment for all follow-up contacts. In addition to participant's contact information, we will be asking participants to designate at least two contact persons who will be aware of their whereabouts should they become unreachable. Participants may be contacted via e-mail for study related correspondence, such as scheduling appointments or to complete surveys.

Research staff will also utilize publicly available websites (i.e. Google, whitepages.com, etc.) to obtain current contact information. Subjects may also be sent greeting cards on holidays and birthdays in an effort to increase participant retention. Subjects may also receive a certificate of recognition at the end of their assigned condition's sessions and/or at the end of the study. The certificate will congratulate the participant (include their name) for completing the appropriate part of the study. We may also include a business card for official study use, such as when meeting or sending correspondence to participants. A study official business card will include study information such as affiliation, study name, contact information, and/or individual study staff names.

Individuals identified as participant contacts will be contacted via phone or mail only when we are unable to reach the participant. Research staff will inform the contact that we are calling from the University of Michigan, or local site as necessary, and that the participant indicated we could contact them in cases in which we had trouble reaching the participant. Research staff will ask the contact person if they have any updated contact information for the participant or if they would pass along a message to the participant on our behalf. Information regarding the nature of the research project will not be shared with the contact person to maintain the confidentiality of the participant. Because this study will be based within treatment clinics, we will also utilize the electronic medical record systems (e.g. MiChart, CPRS) when allowable to monitor patient appointments and to gather contact information. Participants will be asked to sign a HIPAA authorization and/or a release of

information that allows the research team the necessary information. In our past work, we have found that this is a useful way to track changes in patient contact information and to identify good times to make contact with the patient.

Participants will be considered in the study following enrollment and randomization until the completion of the 12-month follow-up or end of the 12-month follow-up window, whichever comes first. Participants will have a total of 6 weeks to complete all study treatment condition sessions. Ideally, condition sessions will be completed by Week 5 of study participation to allow for the timely collection of 1-month data. 1-, 3-, 6-, 9-, and 12-month follow-up data may be collected from the follow-up visit due date \pm 12 weeks (3-months).

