
- (1) the first 8 sessions for each therapist will be assessed for protocol fidelity and the therapist will be provided comments and/or corrective feedback to ensure the above competence metrics are achieved; and
- (2) three sessions for each therapist will be reviewed by a PI or Clinical Supervisor at random each month to ensure ongoing fidelity to the PPMI or EUC condition.

New role play scripts will be developed for portions of the intervention that are specific to buprenorphine retention as well as issues that may arise over the phone or video chat. We have many good training examples from our pilot study and previous work. Materials will be available for those therapists who are not able to attend the initial training or who are hired after any workshops have been completed. Since the material in the study sessions may focus on difficult issues, study therapists will also receive training on how to handle potential crisis situations and adverse events. In addition, the study therapists will receive ongoing supervision of recorded therapy sessions with clinical supervisors throughout the trial.

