10.3.3 Metrics

All data collection forms will be reviewed for accuracy and completeness following their administration by research staff. Any incomplete forms or questions will be assessed by the research staff member with the participant for clarification if possible to minimize the presence of missing data.

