To ensure adherence to study procedures and protocols, the Project Managers will meet on a weekly basis with project staff including Research Assistants and Therapists. We have found that weekly meetings with project staff are beneficial for several reasons, including: 1) maintaining project morale throughout the course of the project, which helps to keep the project team intact and ensure consistent productivity, 2) identifying common challenges among staff and brainstorming solutions (e.g., locating space, communicating with hard-to-reach participants), and 3) communicating project protocol changes that impact the whole team (e.g., changes in recruitment strategy, paperwork, etc.). The Data Manager and Analysts will attend when data-related content is discussed in these meetings. These staff meetings are also used for re-training on participant risk assessment and protection of human subjects including data protection, the informed consent process. The PPMI Therapists will meet with [name], [name], or another specified clinical supervisor biweekly for intervention-specific supervision throughout the intervention condition delivery phase of the project. [name], [name], or another specified clinical supervisor will be responsible for listening to intervention condition session recordings for fidelity to the PPMI manual, project risk protocol, and mastery of overall therapeutic delivery.

The project managers will review consent forms, interviews and other source data including case report and tracking forms for accuracy and completeness. Each review will be documented in the Monitoring Log filed in the Regulatory Binder. Data will be reviewed by random inspection of the completed forms by the project managers and any problems detected will be discussed with the PI. In terms of delivery of the PPMI and EUC conditions, therapists and research staff will receive standardized training in conducting both treatment conditions (for details see Section 5.1 “Conditions, Administration, and Duration above). Adherence to PPMI therapy techniques will be monitored using recordings and individual supervision. If session content drift is observed, the therapist or research staff member will

be retrained.

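### The assessor blind claimed in section 6.2.3 is not protected by the plan's own procedures, chiefly because of the 1-month survey on session content

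*Combined protocol and SAP*

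**What the plan says.** Section 6.2.3 (Blinding) makes two promises about knowledge of the arm. For collectors: "Data collectors responsible for the collection of follow-up data (post-enrollment data) (i.e. research assistants, project managers, or other study staff) will remain blind". For case review of the longitudinal data: "outcome adjudicators, including investigators or project consultants will be blind to condition assignment to ensure unbiased coding of data". It also blinds data managers and analysts. Participants and therapists are not blind. The section adds that study staff have no direct part in collecting the 3-month primary outcome, because it comes from weekly self-report.

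Other sections bear on those promises:

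- **Post-treatment survey (6.2.4).** "This survey will ask general questions about their experiences with both the study therapist (therapeutic alliance) and the session content". It is given once, at the first follow-up after the sessions; the schedule in 6.1 places it at 1 month. On its use: "This survey will be used as a supervision training tool for the therapists and research staff". Only the therapists are denied its data.
- **Form checks (10.3.3).** "All data collection forms will be reviewed for accuracy and completeness following their administration by research staff". A research staff member then clarifies incomplete items with the participant where possible.
- **Meetings (10.3.5).** "the Project Managers will meet on a weekly basis with project staff including Research Assistants and Therapists".
- **Session review (5.1).** "three sessions for each therapist will be reviewed by a PI or Clinical Supervisor at random each month". Session adherence data also go to the PI and project managers monthly (9.2.1 and the table in 10.3.5).
- **Randomisation (6.2.2).** Project managers randomise each participant from the biostatistician's sequence and tell the therapist the condition.
- **Primary measure (9.5.1).** Weekly surveys guide the TLFB interview at 1 and 3 months, and the TLFB is the main measure for analysis.

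**The concern.** The primary event is a run of 7 or more consecutive calendar days without buprenorphine (9.5.1), so one recalled day can decide whether an event is recorded. The day count comes from an interviewer-led calendar. Where the TLFB and the weekly surveys are both available, section 9.6 has them compared and a judgement made about what was actually taken. Participants know their arm, and section 6.2.4 excludes urine tests as primary outcome data. Blind interviewers and adjudicators are therefore the main safeguard at the point where the outcome is collected and coded. If they can learn the arm through routine study work, that safeguard exists only as a statement. Eight CBT sessions and two short brochure calls are easy to tell apart from a participant's comments on session content.

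**Working it through.** No figure in the plan bears on this point, so the check sets what 6.2.3 promises against what each role is given elsewhere.

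| Role said to be blind | Access given elsewhere | Separation stated |
|---|---|---|
| Research assistants | Post-treatment survey at the first follow-up (6.2.4), form checks with the participant (10.3.3), weekly meeting with therapists (10.3.5) | None. Order of survey and TLFB, mode, and who checks are not given |
| Investigators as adjudicators | A PI may review recordings (5.1); the PI sees adherence monthly (9.2.1, 10.3.5) | Recordings carry no study ID and are edited (11.3). Nothing for adherence data |
| Project managers | Randomise and announce the condition (6.2.2); review adherence monthly (9.2.1, 10.3.5) | None. This contradicts 6.2.3 directly |

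**Survey.** Follow-ups are in person where possible, but may be by phone, video, online or mailed paper (6.2.4). If the outcome interviewer administers the survey or clarifies a gap in it, that person can learn the arm at 1 month. The 3-, 6-, 9- and 12-month TLFBs come afterwards, and the 3-month one closes the primary window. If the survey precedes the TLFB on the day, the 1-month interview is exposed too. Whether the same person conducts later visits is not stated, so this gives the timing of possible exposure but not the number of participants.

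**Staff role in the primary outcome.** Section 6.2.3 says staff are not directly involved. Section 9.5.1 makes the staff-led TLFB the main measure, and 6.2.4 lets research assistants take the weekly surveys by phone. The statement in 6.2.3 does not match either.

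**Adherence data.** EUC has 2 sessions and PPMI has 8. If adherence is shown by participant, any count above 2 identifies PPMI.

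**Illustration of stakes (assumed, not from the plan).** Take no true effect, 100 per arm and 50% discontinuation in each, and let a share m of PPMI discontinuations go unrecorded. Then:

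- recorded PPMI risk p = 0.5 × (1 − m)
- apparent HR = ln(1 − p) / ln(0.5)
- events E = 100 × (0.5 + p)
- d = √(E/4) × |ln HR|
- false-positive rate = Φ(d − 1.96) + Φ(−d − 1.96)

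For m = 10%: p = 0.45, HR = 0.862, E = 95, d = 0.72, rate = 11.1%.

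| m | Apparent HR | False-positive rate |
|---|---|---|
| 0% | 1.00 | 5.0% |
| 5% | 0.93 | 6.5% |
| 10% | 0.86 | 11.1% |
| 15% | 0.80 | 19.1% |
| 20% | 0.74 | 30.5% |

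The same Schoenfeld form, applied to the design in 9.2 (50% EUC events, HR 0.5, N = 200), gives 79.3 expected events and 87.0% power. That agrees with the stated figure of more than 85%, which this point does not affect.

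**The case against.** The case against is substantial.

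- **Survey.** It is self-report (5.1) and can be done online or on mailed paper. No text says the TLFB interviewer reads it. Since therapists are denied the data, its training use may be in summary form, and in 10.3.5 research staff named alongside therapists are those trained to deliver sessions. This weakens the route but does not close it. Nothing requires self-completion, fixes the order, or keeps the outcome interviewer from the form or its check.
- **Weekly meeting.** The listed topics (morale, common challenges, protocol changes) need not reveal an allocation. Every therapist delivers both arms, so knowing the therapist does not give the arm. PPMI supervision already has its own biweekly meeting. This stands, and the meeting is a weaker channel.
- **Adjudication.** It occurs only if needed, and 6.2.3 mentions it for the longitudinal data. Unlabelled, edited recordings reduce the risk from session review. This also stands, but it does not cover adherence data.
- **Discretion.** The weekly 7-day calendar and the direct question about a 7-day gap limit the interviewer's latitude, though only for weeks in which the survey was completed.
- **Operating manuals.** Procedural detail is deferred to them (4.3, 5.2, 10.3.5), and they may contain safeguards not seen here.

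A reader might go further and infer three things that the documents do not support. The first is that the blind is bound to fail; exposure depends on mode, order and staffing that are not stated. The second is that the investigators who adjudicate are the ones who audit recordings; reviewers are a PI or a clinical supervisor, adjudicators are investigators or consultants, and overlap is permitted but not stated. The third is that the assessor blind is the trial's only one; 6.2.3 also blinds data managers and analysts.

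**Conclusion.** The point holds in a limited form: the assessor blind is claimed but not protected. The post-treatment survey is the main route, because following the plan as written can show the interviewer the arm before the 3-month TLFB. The joint meeting and the possible overlap of adjudicator and reviewer are secondary. The project managers are the one role for which the plan contradicts itself outright.

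The size of any bias cannot be derived from the documents. The illustrative range of 6.5% to 30.5% false positives rests wholly on the assumed 5% to 20% under-recording in one arm, and shows only that modest differential recording would matter. This is a cheap improvement to make. It is not evidence that the outcome data will be biased.

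**What to change.** 1. Have the post-treatment survey self-completed by REDCap link or sealed paper form, released only after that visit's TLFB is locked. Handle completeness by REDCap validation, or by staff who neither collect outcomes nor act as study therapists, since 6.2.4 bars therapists from the data. Give outcome interviewers no participant-level survey data.
2. Keep participant-level session matters out of meetings that outcome collectors attend, and use the existing supervision meeting for them.
3. Limit adjudication to investigators or consultants who do not see recordings, participant-level adherence or allocation, working from coded calendars.
4. Remove project managers from outcome collection, and amend the list of blind collectors in 6.2.3 to match.
5. Record the interviewer's guess of arm and any unblinding at 3 and 12 months.
6. Correct the statement in 6.2.3 that staff are not directly involved in collecting the primary outcome, so that it agrees with 9.5.1.

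The cost is procedural wording, a change in survey order and some separation of tasks among existing staff, with no added visits. Completeness of the post-treatment survey may fall slightly.
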